9.0 Safety Analyses

9.1 General Considerations

Refer to Section 8.1 for general considerations apply to both effectiveness and safety analyses.

- For CP, safety analyses will be performed on the safety population, using as-treated grouping.
- For TP, safety summaries will be performed on the VT population, using as-treated grouping.
- For MP, safety summaries will be performed on the VMT population.
- Adverse events (AEs) will be coded using the Medical dictionary for Regulatory Activities (MedDRA). The actual version of the MedDRA coding dictionary will be noted in the statistical tables and clinical study report.

9.2 Adverse Events

9.2.1 Treatment-Emergent Adverse Events

An AE will be considered a treatment-emergent adverse event (TEAE) if the AE began or worsened (increased in severity or became serious) on or after the first administration of study intervention (i.e., on or after study Day 1 defined in Section 7.1).

A treatment-emergent serious adverse event (TESAE) is defined as a serious adverse event (SAE) that is also a TEAE.

9.2.2 Adverse Event Overview

TEAEs will be summarized by treatment group for CP using the safety population. TEAEs will also be summarized by treatment group for TP and MP using the VT and VMT populations, respectively as described in Table 9. The summaries will be presented using number and percentage of participants with TEAEs as well as the number of events. Additional summaries may be provided when applicable.

An overall summary of TEAEs will be presented as described in Table 9.

Treatment-related AEs will be summarized by duration, severity, time to onset on/after the most recent treatment, and outcome.

The duration of an AE is defined as the end date of AE minus the start date of AE plus 1.

For participants who received maintenance treatment, their AEs reported during the first 6 months from the initial treatment will be summarized and presented in parallel with AEs reported during the maintenance treatment period. The summary for the initial treatment will be presented for participants who received initial treatment only and participants who received both initial and touch-up treatments.

If more than 1 AE is coded to the same preferred term for a participant, the participant will be counted only once for that preferred term using the most severe and most related occurrence for the severity and relationship to study intervention summaries, respectively.

If the severity of a TEAE is missing, the maximum severity will be assigned to the event for the summary on severity. The value will be displayed as missing in the data listing.

If the relationship to the study intervention is missing for a TEAE, the event will be considered related to the study intervention for the summary. The value will be displayed as missing in the data listing.

Listings of all AEs, TESAEs, TEAEs leading to discontinuation, and death will be presented.

Table 9. TEAE Summaries

Endpoint	Description	Timing	Methodology
Overall summary	Overall summary only for the following categories: 
 • TEAEs • Treatment-related TEAEs • Treatment-related TEAEs at injection site • Treatment-related TEAEs not at injection site • TESAEs • Treatment-related TESAEs • Treatment-related TESAEs at injection site • Treatment-related TESAEs not at injection site • Discontinued due to TEAEs • AESIs • Treatment-related AESIs • Deaths • TEAEs related to COVID-19 infection 	CP, TP, MP	Frequency counts and percentages
TEAEs	
 • By SOC and PT • By SOC, PT, and maximum severity 	CP, TP, MP	Frequency counts and percentages
Treatment-related TEAEs	
 • By SOC and PT • By SOC, PT and maximum severity • By duration, time to onset from the most recent treatment, and outcome and categorized by severity 	CP, TP, MP	Frequency counts and percentages
TESAEs	By SOC and PT	CP, TP, MP	Frequency counts and percentages
AEs leading to study discontinuation	By SOC and PT	CP, TP, MP	Frequency counts and percentages

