| Adverse events e (TI)   |                                  | Con     | tinuous mor | nitoring |   |
| Concomitant medications and concurrent procedures
(TI)  | Continuous monitoring            |         |             |          |   |

a month = 30 days

a The follow-up visit schedule is based on the date of the last study intervention (ie, if no touch-up treatment is performed, the Month 1 visit occurs 30 days after initial treatment; if touch-up treatment is performed, the Month 1 visit occurs 30 days after touch-up treatment).

b At the Month 13 visit, participants will be offered a maintenance treatment after completion of the Month 13 visit. Participants who accept maintenance treatment will undergo the additional procedures specified in Table 1-4. Participants who do not accept maintenance treatment will exit the study after the Month 13 procedures are completed.

c If a participant withdraws for any reason prior to the final study visit, attempts will be made to perform assessments at an exit visit.

d For female participants of childbearing potential. A female is not considered of childbearing potential if she has been postmenopausal for at least 1 year or does not have a uterus at the time of study entry.

e Will include a general, nondirected question about vision symptoms.

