#### 6.1. **Study Intervention Administered**

| Study Intervention
Name               | VOLUMA XC  | Delayed Treatment  |
|--|--|--|
| Device                                   | JUVÉDERM VOLUMA XC   | Same   |
| Dose Formulation                         | 20 mg/mL HA crosslinked with BDDE
+ 0.3% lidocaine (w/w gel)  | Same   |
| Route of
Administration               | Deep injection (supraperiosteal plane), injected with
a 27 G 1/2" or 25 G 1" needle in the temple area  |  |
| Packaging and
Labeling                | Study intervention will be provided in prefilled
syringes. Each syringe will be packaged with
27 G 1/2" needles for injection in a thermoform tray.
The 25 G 1" needles will be provided separately.
One or more trays will be packaged in a kit. Each kit
and thermoform tray will be labeled as required per
country requirements. | Same   |
| Manufacturer                             | Allergan
[name]   | Same   |
| Number and
Timing of
Interventions | Initial treatment
30 days after initial treatment: Optional touch-up
Month 13: Maintenance treatment   | After Month 3 of control period:
Optional initial treatment
30 days after optional initial
treatment: Optional touch-up |
| Volume Per
Intervention               | Initial and touch-up combined: up to 3 mL/temple
Maintenance treatment: up to 2 mL/temple
Any single treatment: up to 2 mL/temple  |  |

Table 6-1

[figure not shown]

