5.0 Participant Disposition

5.1 Study Period

The study periods are defined below in Table 2 for VOLUMA XC group and control group. For VOLUMA XC group, the Treatment Period (TP) is the Control Period (CP) plus the Post-Control Period (PCP). For participants in the control group, the TP starts on the date of optional treatment and ends on the same day as the study exit.

Table 2. Definition of the Control, Treatment and Maintenance Treatment Periods by Analysis Group (as-randomized for effectiveness or as-treated for safety)

Analysis Group	Period	Analysis Group Label	Start Date	End Date
VOLUMA	CP	VOLUMA XC	Initial treatment date	
The end date is the date of the Month 3 assessment:
 
 • If multiple assessments fall into Month 3 window, the date of the assessment included in the Month 3 analysis will be used as end date. • For participants who exit before Month 3, the end date is study exit date. • For participants with a missing assessment at Month 3, the end date is the target day for Month 3 (90 days from preceding treatment).
	TP	VOLUMA XC	Initial treatment date	Date of maintenance treatment or the study exit date, whichever is earlier
	MP	VOLUMA XC	Maintenance treatment date	Study exit date
Control	CP	Control	Randomization date	
For participants who do not receive optional treatment:
 
 • If multiple assessments fall into Month 3 window, the date of the assessment included in the Month 3 analysis will be used as end date. • For participants who exit before Month 3, the end date is study exit date. • For participants with missing assessment at Month 3, the target day for Month 3 (Day 91) will be the end date. 
For participants who receive optional treatment, the end date is the date of optional treatment.

	TP	VOLUMA XC Post-Control	Optional initial treatment date	Study exit date

The start and end of treatment periods listed above for the mis-treated participants (ie., randomized to treatment and did not receive VOLUMA XC or randomized to control and was treated with VOLUMA XC prior to the primary timepoint) will be determined based on the treatment received.

For CP, effectiveness analyses and baseline characteristics will be performed on the mITT population using the "as-randomized" assignment.

For TP, effectiveness and safety summaries will be performed on the VT population by treatment group.

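### In the maintenance safety comparison, the initial-course column covers only 140-150 days after the last injection in touched-up participants, while the maintenance column runs to its Month 6 exit

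*SAP*

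**What the plan says.** SAP 9.2.2 plans a side-by-side safety display in participants who received maintenance: "AEs reported during the first 6 months from the initial treatment will be summarized and presented in parallel with AEs". The second set of events is the one from the maintenance period. The initial-course side is shown for participants with the initial treatment only and for those who also had a touch-up. Both groups have the same starting point, the initial treatment.

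SAP Table 2 (Section 5.1) starts the maintenance period at the "Maintenance treatment date" and ends it at study exit. Protocol Table 1-4 plans that exit at Month 6 after maintenance, ± 15 days.

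Protocol Table 1-3, footnote a, counts initial-course follow-up from the last study intervention: "if touch-up treatment is performed, the Month 1 visit occurs 30 days after touch-up treatment". The SAP mostly follows the same convention. Table 2 sets the Month 3 target for the VOLUMA XC group at "90 days from preceding treatment". Section 8.3.3 times the treatment group's Month 3 from the latest of randomization, initial and touch-up treatment. Table 9 measures time to onset from the most recent treatment.

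**The concern.** A reader will take the two columns as like for like: the same people, about six months after the first course and about six months after a repeat. For touched-up participants the columns match in total length but not in time after the last injection.

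An event that starts, say, 160 days after the touch-up is left out of the initial-course column. The same event 160 days after maintenance is counted. Scheduled questioning about AEs differs too: Table 1-3 has no planned contact between Month 3 and Month 6, and the Month 6 visit lies outside the initial-course window. The AE inquiry in both follow-up periods includes a general question about vision symptoms, and visual disturbance is the AE of special interest.

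At stake is how far this display can show whether later events after a repeat injection resemble those after the first course.

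**Working it through.** **Inputs**
- Length of a month: "a month = 30 days" (Protocol Table 1-3). SAP 9.2.2 does not give 6 months in days, so 6 × 30 = 180 is an assumption, tested below.
- Touch-up: 30 days after the initial treatment, window + 10 (Protocol Section 6 and Table 1-2), so day 30 to 40.
- Initial-course visits after the last injection: Month 3 at 90 ± 7 days and Month 6 at 180 ± 15 days (Table 1-3).
- Maintenance exit: 180 ± 15 days after the maintenance injection (Table 1-4), so day 165 to 195.

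**The plan's own figures.** The SAP's 90-day target for Month 3 agrees with 3 × 30. Protocol 4.1 gives up to 21 months for the treatment group: 1 (screening) + 1 (treatment) + 13 + 6 = 21. Counting follow-up from the initial injection would give 1 + 13 + 6 = 20. The stated total therefore confirms that follow-up is counted from the end of the treatment period.

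**Touched-up participants, 180-day window from the initial treatment**

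| Quantity | Touch-up day 30 | Touch-up day 40 |
|---|---|---|
| Days covered after last injection (180 − touch-up day) | 150 | 140 |
| Shortfall against 180 | 30 (30/180 = 17%) | 40 (40/180 = 22%) |
| Month 3 visit, days from initial (touch-up day + 90 ± 7) | 113-127 | 123-137 |
| Month 6 visit, days from initial (touch-up day + 180 ± 15) | 195-225 | 205-235 |
| Days by which Month 6 visit misses day 180 | 15-45 | 25-55 |

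The maintenance column covers 165-195 days after its injection. The difference in cover after the last injection therefore runs from 165 − 150 = 15 to 195 − 140 = 55 days, and is nominally 30-40.

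**Is the miss sensitive to the assumptions?** For the earliest in-window Month 6 visit to fall by day 180, the touch-up would have to be on day 180 − 165 = 15 or before. With six calendar months (181-184 days), the shortfall is 26-39 days and the earliest Month 6 visit, day 195, is still outside.

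**No touch-up.** The Month 6 visit falls on day 165-195, so it is cut only when later than day 180, by at most 195 − 180 = 15 days.

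**Meaning of reported.** If AEs are selected by onset, those starting after day 180 are omitted, that is, more than 140-150 days after the touch-up. If they are selected by report date, AEs that began earlier but were first elicited at Month 6 are omitted as well.

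**What the initial-course column has more of.** For a touched-up participant it holds seven planned post-injection contacts: 3-day call, 14-day visit, 30-day/touch-up visit, second 3-day call, second 14-day visit, Month 1 and Month 3. The maintenance column has five: 3-day call, 14-day visit, and Months 1, 3 and 6. The initial-course column also spans two injection sessions and two e-diary periods, with a combined volume of up to 3 mL per temple (Protocol Table 6-1). Maintenance is one session: "Maintenance treatment: up to 2 mL/temple".

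**The case against.** Anchoring at the start of each course is defensible. It nominally matches total observation time, 180 days against 165-195. A window from the last injection stretches the touched-up course to 210-220 days. This stands, and it is why the planned summary should be kept.

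A reader might infer that the display must make maintenance look worse. The documents do not support that. The extra session, contacts and volume could raise event counts in the initial-course column. Everyone in that column reached Month 13, whereas early exit can shorten the maintenance column. No rate of late events is given. These influences partly oppose one another, so the net direction cannot be settled.

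A reader might also infer that events elicited at Month 6 are certainly dropped. That needs the report-date reading. SAP 9.2.1 defines treatment-emergent events by when they began or worsened, which favours onset, and the table specifications are in a separate document. The wording is ambiguous, but onsets after day 180 are excluded on either reading.

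Nor are any events lost from the study report. The treatment period runs to the maintenance date or study exit, so the omitted events stay in its tables and in the listing of all AEs. Table 9 also gives time to onset from the most recent treatment. That table does not replace the display: it is limited to treatment-related events and uses all VOLUMA XC-treated participants, not the maintained participants alone. The split by touch-up status shows who is affected but leaves the window unchanged.

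**Conclusion.** The point holds as a limited misalignment. In touched-up participants the initial-course column covers 140-150 days after the last injection, nominally 30-40 days fewer than the maintenance column, and excludes the Month 6 visit. Only late events after the last injection are clearly under-covered.

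This rests on 30-day months and on touch-up and Month 6 visits within their protocol windows. How many participants are affected depends on a touch-up rate that the visible text does not give. The display is descriptive, with no test or decision rule attached, and the primary effectiveness analysis is untouched. The change is worth making because it is cheap and no other visible table gives this comparison in the same participants.

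**What to change.** In SAP 9.2.2:
- State that AEs are selected by onset date, so that an event first reported at the Month 6 visit counts if its onset is in the window.
- Apply one window to both columns: onset within 180 days after the last treatment of that course (touch-up if given, otherwise initial; maintenance for the repeat course).
- For touched-up participants, show onset before touch-up and onset within 180 days after touch-up as separate rows. The second row is the one to read against maintenance.
- Keep the planned summary of 6 months from the initial treatment, and the split by touch-up status.

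The cost is SAP wording, one derived flag and an extra row. No new data are needed: Month 13 is planned at 13 × 30 = 390 days after the last injection, 375 at the earliest, so 180 days after touch-up is well inside existing follow-up. The downside is a total initial-course window of 30 + 180 = 210 to 40 + 180 = 220 days for touched-up participants, to be stated in a footnote. The same footnote should say that a maintenance exit visit may fall as early as day 165.

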4.0 Analysis Populations

The analysis populations will consist of participants as defined in Table 1 below:

Table 1. Analysis Sets

Population	Definition	Study Intervention
mITT	All randomized participants who have non-missing baseline assessment on the AHS for both temples. This will be used as the full-analysis-set population.	As randomized
Observed Primary Endpoint (OPE)	All mITT population participants who have a Month 3 assessment on the AHS for both temples.	As randomized
Safety	All participants who are randomized and received study intervention (VOLUMA XC or no-treatment control).	As treated
VOLUMA XC Treated (VT)	All safety population participants who received VOLUMA XC treatment as initial treatment at the beginning of the Control Period, or as optional treatment after the Control Period	As treated
VOLUMA XC Maintenance Treatment (VMT)	All safety population participants who received VOLUMA XC maintenance treatment	As treated

The number of participants in each of the 5 study populations (mITT, OPE, Safety, VT and VMT) will be summarized by treatment group, if applicable.

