8.0 Effectiveness Analyses

8.1 General Considerations

- This section applies to both effectiveness and safety analyses when applicable.
- To account for different timing of VOLUMA XC treatment and comparable time frames of data collection and to enhance interpretability of effectiveness and safety analyses, the statistical analyses will be performed by the study periods defined in Table 2.
- For CP, effectiveness analyses and baseline characteristics will be performed on the mITT population using the as-randomized assignment.

- For TP, effectiveness and safety summaries will be performed on the VT population, using as-treated grouping.
- For MP, effectiveness and safety summaries will be performed on the VMT population.
- Study day refers to Day 1 regardless of study period (e.g., CP, TP, MT).
- The baseline for effectiveness and safety parameters will be the last non-missing assessment prior to or on Day 1, i.e., the latter of randomization or initial injection in Control Period. Day 1 is defined as the day on which the study intervention (VOLUMA XC or no-treatment) is first received.
- The change from baseline values will be computed as the postbaseline value minus the baseline values.
- For vision assessments, baseline will refer to the most-recent measurement just prior to the most-recent treatment.
- Continuous variables will be summarized by number of participants with observed values (n), mean, standard deviation (SD), median, 1st and 3rd quartiles (Q1, Q3), minimum (min), and maximum (max). Categorical variables will be summarized by the number of participants with observed values or events (n) and the percentage of participants with observed values or events.
- All statistical hypothesis tests will be performed at the 2-sided, 5% significance level, unless stated otherwise.
- All CIs will be 2-sided 95% CIs, unless stated otherwise.
- All statistical analyses will be performed using SAS Version 9.4 or subsequent.

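### SAP 9.2.2 would count a blank causality in a control who has not been injected as a treatment-related event

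*SAP*

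**What the plan says.** SAP Section 9.2.2 sets the rule: "If the relationship to the study intervention is missing for a TEAE, the event will be considered related to the study intervention for the summary". A second sentence keeps the value visible as missing in the data listing. Neither sentence restricts the rule by group or by whether the participant has been injected.

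Four other parts of the SAP decide who the rule reaches:

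- **Safety population (Section 4.0, Table 1):** "All participants who are randomized and received study intervention (VOLUMA XC or no-treatment control" and so on. Being a no-treatment control counts as having received study intervention.
- **Day 1 (Section 8.1):** "Day 1 is defined as the day on which the study intervention (VOLUMA XC or no-treatment) is first received". A control reaches Day 1 without a device.
- **TEAE (Section 9.2.1):** an event that begins or worsens "on or after the first administration of study intervention (i.e., on or after study Day 1 defined in Section 7.1".
- **Control-period (CP) tables (Sections 9.1 and 9.2.2):** "For CP, safety analyses will be performed on the safety population, using as-treated grouping", and "TEAEs will be summarized by treatment group for CP using the safety population".

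Table 9 then lists treatment-related TEAEs, serious TEAEs and adverse events of special interest for the control, treatment and maintenance periods alike. Related events are also split by location, with a row for "Treatment-related TEAEs at injection site" and one for those elsewhere, and by time since the latest treatment.

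**The concern.** Counting a blank as related is a cautious default for someone who has been injected, because it can only raise the apparent risk of the device. For a control who has not been injected the same default works the other way. No device has been given, so the imputed entry asserts a relationship to something that has not happened. It also raises the comparator's related rate and, with the treatment column unchanged, narrows the contrast with the device group.

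At stake is the accuracy of one column, the control-period Control column, in the treatment-related rows of a descriptive safety table. The imputed entry also cannot be placed sensibly in the rest of Table 9, since the participant has no injection site and no treatment from which to count time to onset.

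**Working it through.** The plan states no figure on this point, so there is none to reproduce. The check traces the text first and then sizes one affected participant.

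**Text trace**

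1. Controls who have not been injected are in the safety population (SAP Table 1).
2. They have a Day 1 (SAP 8.1). Section 9.2.1 refers to Section 7.1 for that definition, but it stands in 8.1; the cross-reference should be corrected.
3. Their adverse events from Day 1 onward are therefore TEAEs (SAP 9.2.1).
4. Control-period TEAEs are shown by group as treated (SAP 9.1 and 9.2.2), so there is a Control column. As-treated grouping moves a control injected early by mistake out of that column. It leaves the other controls in place.
5. Table 9 includes the treatment-related rows for the control period.
6. The missing-causality rule applies to any TEAE. No visible text exempts events that precede a first injection.

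So a blank causality in such a control is counted as related.

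**The column is not strictly free of device exposure.** Under SAP Table 2, a control who takes optional treatment has a control period that ends on the optional treatment date, which is also the start of that participant's treatment period. An event that day, after injection, could be genuinely device-related and still fall in the control period. The dividing line therefore has to be the injection date and not the arm.

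**Size of one entry**

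Inputs: 171 randomized at 2:1 (protocol synopsis, Number of Participants), giving 171 × 2/3 = 114 treatment and 171/3 = 57 control. It is assumed that all of them enter the safety population in their randomized group.

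| Participants with an imputed related event | Control (n = 57) | Treatment (n = 114) |
|---|---|---|
| 1 | 1/57 = 1.75% | 1/114 = 0.88% |
| 2 | 2/57 = 3.51% | 2/114 = 1.75% |
| 3 | 3/57 = 5.26% | 3/114 = 2.63% |

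One blank weighs twice as much in the Control column. The exact (Clopper-Pearson) 95% interval for 1/57 is 0.04% to 9.39%.

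**How often it might happen**

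The documents give neither a control TEAE count nor a blank rate, so both are assumed: m control TEAEs, each blank with probability q independently. The expected number of false related events is m × q, and the chance of at least one is 1 − (1 − q)^m.

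| m | q | Expected | Chance of at least one |
|---|---|---|---|
| 5 | 1% | 0.05 | 4.9% |
| 5 | 5% | 0.25 | 22.6% |
| 10 | 2% | 0.20 | 18.3% |
| 20 | 1% | 0.20 | 18.2% |
| 20 | 5% | 1.00 | 64.2% |

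If each event falls in a different participant, the expected addition to the Control rate runs from 0.05/57 = 0.09 to 1.0/57 = 1.75 percentage points.

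**After the fix:** blanks before a first injection contribute 0/57, and the rule still applies in full to injected participants.

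**The case against.** The strongest reply is that this is a conventional fallback that should almost never operate. The protocol (Appendix 10.7.4, Assessment of Causality) obliges the principal investigator to assess and document causality for every event. The data listing still shows the value as missing, so an imputed control entry could be traced. Table 9 plans counts and percentages only, and no visible text plans a between-group test on adverse events. The all-TEAE comparison with no treatment is untouched by the rule, and device safety is also summarized in populations in which everyone received VOLUMA XC. Finally, the table specifications are in a separate document that may footnote or suppress the Control cells. All of this stands as an argument about weight. None of it changes what the SAP rule does when a blank occurs, and the SAP itself contains no exemption.

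A reader might infer more than the documents support:

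- **That blanks are more common in controls, because the site has nothing to relate the event to.** This is plausible, but no passage says so. Scenarios in which half or all control fields are blank would amount to a wholesale breach of the investigator's duty and are not a fair expectation.
- **That the treatment-related rows are the main safety comparison with no treatment.** The documents do not give them that standing.
- **That every control-period related entry in the Control column must be false, so the whole column should be marked not applicable.** The shared date in Table 2 allows a genuine event on the day of optional treatment. A blanket entry would hide it and would override causality that the investigator did record.

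**Conclusion.** Wrong as written, and minor. Whenever the rule meets a blank for a control who has not been injected, it produces an entry that has no device exposure behind it and that the related rows of Table 9 cannot place. Each such control adds 1.75 percentage points at the planned group size. The likely total is small: about 0.05 to 1.0 false events under the assumed 5 to 20 control TEAEs and 1% to 5% blank, and none if causality is always completed. No planned hypothesis test is affected. The conclusion rests on the visible SAP text; the separate table specifications could not be checked.

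**What to change.** In SAP Section 9.2.2:

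- Limit the missing-causality rule to TEAEs with onset or worsening on or after the participant's first VOLUMA XC injection.
- For earlier events, query the field. If it stays blank, show the relationship as missing or not applicable and do not count the event as related.
- Leave every causality recorded by the investigator as reported, and do not set the whole Control column to not applicable.

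Keying on injection date also covers participants not treated as randomized and events on the day of optional treatment. In the same edit, point the Day 1 reference in Section 9.2.1 to Section 8.1.

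The cost is a short addition to the SAP, one programming condition, and a data query for any blank before a first injection. The treatment of blanks in injected participants does not change.
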